### *Circulating biomarkers*

Many classical biomarkers (e.g., C-reactive protein, N-terminal pro-B-type natriuretic peptide (NT-proBNP) and troponin (TnI)) were shown to be potential biomarkers for cardiac damage after radiotherapy. In addition, circulating inflammatory cytokines also signified tissue inflammation. Furthermore, it was shown that irradiation induced acute endothelial activation or dysfunction that can be observed many weeks after irradiation and resulting in a pro-inflammatory endothelial phenotype.

Another hypothesis to explore is that the irradiation may be responsible for an increase in the circulating levels of certain miRNAs expressed by cells of the heart tissue. Currently, the potential function of extracellular miRNAs is being studied intensively, and the first studies have confirmed that miRNAs may indeed function in cell-to-cell communication. Many studies have reported the use of miRNAs as circulating biomarkers for diagnosis or prognosis of cardiovascular diseases. Although many of those studies still require replication in multiple independent study populations, the results so far strongly suggest that some plasma miRNAs are quite specific for cardiovascular pathologies and may be useful for diagnostic and monitoring purposes.

The complex and multifactorial nature of atherogenesis and development of atherothrombotic complications involves numerous interactions between various cell types inside the vascular wall (e.g. macrophages and smooth muscle cells) and in the blood (e.g. leukocytes and platelets). One relatively recent advance in this area is the discovery of circulating microparticles. High levels of circulating microparticles found in many cardiovascular diseases demonstrate the importance of platelet, monocyte and endothelial activation and could condition remote sustainability illnesses. The above described imaging studies have shown that early subclinical cardiac changes occur in BC patients after RT. Additionally, classical cardiac biomarkers have been shown to be potential candidates to monitor cardiac damage after radiotherapy. However, primary and secondary prevention measures require (exact) knowledge on the relationship between dose exposure to specific cardiac structures and (the timing of) early subclinical cardiac changes and their occurrence in time.

So far little has been done on elucidating the specific relationships between doses to cardiac structures and subsequent early cardiac toxicity in the published imaging or biomarker studies.

## **2.2. Summary and proposed study**

The above described imaging studies have shown that early subclinical cardiac changes occur in BC patients after RT. Additionally, classical cardiac biomarkers have been shown to be potential candidates to monitor cardiac damage after radiotherapy. However, primary and secondary prevention measures require (exact) knowledge on the relationship between dose exposure to specific cardiac structures and (the timing of) early subclinical cardiac changes and their occurrence in time. So far little has been done on elucidating the specific relationships between

doses to cardiac structures and subsequent early cardiac toxicity in the published imaging or biomarker studies.

MEDIRAD-EARLY HEART therefore aims to determine early (i.e., within 24 months) cardiovascular changes after BC radiotherapy using imaging and circulating biomarkers and to determine the relation with radiation dose to a variety cardiac structures.

### 3. OBJECTIVES OF THE TRIAL

#### 3.1. General objectives

MEDIRAD-EARLY HEART is part of the MEDIRAD project. The MEDIRAD project aims to enhance the scientific basis and clinical practice of radiation protection in the medical field and thereby addresses the need to understand and evaluate the health effects of low dose ionizing radiation exposure from diagnostic and therapeutic imaging and from off-target effects in radiotherapy.

MEDIRAD will pursue 3 major operational objectives: First, it will improve organ dose estimation and registration to inform clinical practice, optimize doses, set recommendations and provide adequate dosimetry for clinical-epidemiological studies of effects of medical radiation. Second, it aims to evaluate and understand the effects of medical exposures, focusing on the two major endpoints of public health relevance: cardiovascular effects of low to moderate doses of radiation from RT in BC treatment including understanding of mechanisms; and long-term effects on cancer risk of low doses from CT in children. Third, it will develop science-based consensus policy recommendations for the effective protection of patients, workers and the public.

The specific objective of the MEDIRAD-EARLY HEART study is to gain more insight in the relationship between radiation dose distributions to the heart, to different anatomical cardiac substructures, during RT and early cardiovascular changes (within two years).

**Primary objective:** to identify the most important cardiac imaging (ECHO-ST, CT and MRI) and circulating biomarkers of radiation-induced cardiovascular changes arising in the first 2 years after BC RT and to develop Normal Tissue Complication Probability (NTCP) models integrating these biomarkers combined with dose metrics of cardiac structures based on 3D-dosimetry.

**Secondary objectives:**

- To formulate recommendations for implementation of these multivariable NTCP models in primary and secondary prevention strategies to ultimately develop stratified therapeutic and diagnostic approaches (overarching aim of MEDIRAD):
  - Improvement of RT planning techniques to spare cardiac structures, or even selection for proton therapy;
  - First guidelines for cardiac follow up programs in high-risk BC patients;
- To implement a European repository of patient dose and imaging data (overarching aim of MEDIRAD WP2.4.1).

## 3.2. Endpoints

### 3.2.1. Primary endpoints

The primary endpoints are defined as a mean decrease in Global Longitudinal Strain or Global Longitudinal Strain Rate, determined by cardiac ECHO-ST, of at least 2.5% between baseline and 24 months after RT (*Erven et al, Int J Radiation Oncol Biol Phys, 2012; Lo et al, In J Radiation Oncol Biol Phys, 2015*).

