## 1. TWO-PAGE OUTLINE OF THE PROTOCOL

**1.1. Background:** Breast cancer (BC) radiotherapy (RT) leads to coincidental radiation of the heart, resulting in increased risk of a variety of heart diseases. The prevalence of BC survivors at risk of cardiac complications will gradually increase, as the incidence of BC in Europe is still rising while prognosis significantly improved over the last decades. These late cardiac complications have a major impact on quality of life and lead to subsequent morbidity and increased mortality. Therefore, identifying BC patients with the highest-risk of radiation-induced cardiac complications is crucial for developing strategies for primary and secondary prevention, which may contribute to healthy ageing. So far, little has been done on the relationship between dose distribution to different anatomical cardiac structures during RT and early cardiovascular changes that may lead to cardiac complications.

**1.2. Main study objective:** The main objective is to identify and validate the most important cardiac imaging (ECHO-ST, CTCA and MRI) and circulating biomarkers of radiation-induced cardiovascular changes arising in the first 2 years after breast cancer radiotherapy.

**1.3. Study design:** An international multicenter prospective cohort study

**1.4. Endpoints:** The primary endpoint is defined as a mean decrease in Global and Segmental Longitudinal Strain and Strain Rate (GLS/GLSR) of at least 2.5% assessed by cardiac ultrasound 6 to 24 months after RT compared to baseline.

The secondary endpoints are:

- Changes in myocardial function assessed by cardiac ultrasound 6 to 24 months after RT compared to baseline.
- Anatomical changes in coronary artery atherosclerosis (number of coronary segments containing any plaque/stenosis, and calcium score) by cardiac CT 24 months after RT compared with baseline. The endpoint is defined as 15% or greater changes.
- Myocardial changes by MRI 6 to 24 months after RT compared with baseline (morphology, function, tissue characterization by delayed enhancement and pre-/post-contrast T1 mapping). The endpoint is defined as an increase of the mean T1 mapping value of at least 7%.
- Temporal changes in circulating biomarkers at the end of RT and 6 to 24 months after RT compared with baseline. The endpoint is defined as a significant increase or decrease in each biomarker between time points.

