### 1.7. Statistical considerations:

With 250 women, the study will have 80% power, with an  $\alpha=0.05$  to find a mean decrease in GLS/GLSR of at least 2.5%.

The analysis plan is divided into three parts. In the first part a descriptive analysis of the data is done. Differences in biomarkers between unexposed and paired exposed groups (e.g. right vs. left-sided breast RT) at different time points are analysed to generate preliminary hypotheses on effects of RT on the heart. To investigate the time course of continuous variables extracted from ECHO-ST, CT or MRI measurements, mixed regression models are used. In the second part (anatomical) changes in cardiac biomarkers are correlated with dose distribution data. In the third part of the analysis multivariable Normal Tissue Complication Probability (NTCP) models are constructed. An integrative clinical-biological risk score is developed for individual risk prediction.

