## **Exclusion criteria**

- Atrial fibrillation detected during electrocardiogram before radiotherapy
- Abnormal echocardiography before radiotherapy defined as: LVEF<50%; longitudinal strain  $\leq$  -16%; longitudinal strain rate  $<$ -1%, and/or abnormal wall motion
- Presence of myocardial infarction detected during MRI before radiotherapy
- CTCA or cardiac MRI results before radiotherapy requiring revascularisation

▶ See CRF ELIGIBILITY in appendix for further details

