### 9.2. Sample Size

The sample size was based on a statistical power of 80%, an alpha-risk of 5%, the definition of the primary endpoint (a decrease in the global and segmental longitudinal strain or strain rate of at least 2.5%) and baseline measurements hypothesis (mean global longitudinal strain before RT : -16.5%  $\pm$  2.1% from Dalen et al, European Journal of Echocardiography : the Journal of the Working Group on Echocardiography of the European Society of Cardiology. 2010) Considering paired test for comparisons, but also possible lost to follow-up due to death or other reason, the inclusion of 250 women is necessary for EARLY-HEART study.

Centre	Recruitment rate per month	Total number of patients to recruit in 1 year
IRSN	4.2	50
UMCG	5	70
TUM-MED	4.6	55
CCUL	2.1	25
ICO	4.2	50
Total		250

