#### *Stage I: Descriptive analysis*

Means, standard deviations, percentages, ranges and confidence intervals of 95 % are used to summarize:

- The questionnaire medical data;
- The 2D-speckle-tracking echocardiography (ECHO-ST) measurements including strain and strain rate.
- The Coronary computed tomography angiography (CT) measurements including mean number of coronary segments with plaques and/or stenosis, and CAC score (Agatston, Volume), total and per coronary artery;
- The MRI measurements include ventricular function, size of the heart chambers and wall thickness, tissue characterization by delayed enhancement and pre-/post-contrast T1 mapping of the left ventricle;
- The measurements of all biomarkers;
- Dose distribution to the several heart substructures including ventricles and coronaries arteries.

Paired non-parametric tests (Wilcoxon signed rank test to compare medians, McNemar and Bowker to compare paired proportions). The correlation between the different covariates will be investigated using the Spearman's rank correlation coefficient.

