## Appendix

### LOCAL CRF ECHO-ST

**Inclusion Number:** .....

**Date of the visit** : .....

**Date of Birth:** .....

Name and version of the of the ultrasound system:

- General Electric Health Care , version:
- Philips, version:
- Siemens, version:
- Toshiba, veesion
- Other to precise:

Precise if it is : before radiotherapy

6 months after the end radiotherapy

2 years after the end of radiotherapy

- Global longitudinal strain: .....
- Segmental longitudinal strain (Segment 1 to 16) : .....
- Global longitudinal strain rate: .....
- Segmental longitudinal strain rate (Segment 1 to 16) : .....
- Global radial strain : .....
- Segmental radial strain (Segment 1 to 16) : .....
- Global radial strain rate: .....
- Segmental radial strain rate (Segment 1 to 16) : .....
- Left ventricular ejection fraction using Simpson's biplane method: .....
- Left ventricular end-diastolic volume using Simpson's biplane method: .....
- Left ventricular end-systolic volume using Simpson's biplane method: .....
- Left-ventricular end-diastolic diameter using M-mode: .....
- Left ventricular mass measured according ASE/EAE guidelines: .....
- E/A wave ratio : .....
- E/Ea wave ratio (lateral annulus) : .....
- TAPSE (tricuspid annular plane systolic excursion) : .....
- Tricuspid annular S wave : .....
- Pulmonary artery systolic pressure (based on the peak tricuspid regurgitation velocity estimate and by assuming a right atrial pressure of 5 mmHg) : .....
- Left ventricular outflow tract diameter: .....
- Left ventricular outflow tract velocity time integral: .....
- Heart rate: .....
- Cardiac output measured by multiplying heart rate by stroke volume: .....

**In case of abnormal echocardiography before radiotherapy defined as: LVEF<50%; longitudinal strain  $\leq$  -16%; longitudinal strain rate <-1%, and/or abnormal wall motion, the patient should be excluded of the study (exclusion criteria )**

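### The primary endpoint has three conflicting definitions and no designated analysis, baseline selection on strain can shift the before-after mean by itself, and the blood-marker endpoints have no error control

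*Combined protocol and SAP*

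**What the plan says.** **Endpoint.**
- Section 3.2.1: "mean decrease in Global Longitudinal Strain or Global Longitudinal Strain Rate, determined by cardiac ECHO-ST, of at least 2.5% between baseline and 24 months".
- Section 1.4, also as a mean fall: "Global and Segmental Longitudinal Strain and Strain Rate (GLS/GLSR) of at least 2.5% assessed by cardiac ultrasound 6 to 24 months after RT".
- Section 9.2, as the basis of the sample size: "a decrease in the global and segmental longitudinal strain or strain rate of at least 2.5" per cent, with no time point.

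**Analysis.** Section 9.2 gives 80% power and a 5% alpha, without sidedness, and adds "Considering paired test for comparisons, but also possible lost to follow-up due to death or other reason". It states neither an SD of change nor a loss rate. Section 9.3, Stage I (descriptive) lists the "Wilcoxon signed rank test to compare medians". Section 1.7 and Stage II plan mixed regression models for the time course of continuous echocardiographic variables. None of these is tied to the primary endpoint.

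**Role of 2.5%.** Sections 1.7 and 9.2 use it as the effect to detect. Sections 1.4 and 3.2.1 also write it into the endpoint definition.

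**Baseline selection.** The exclusion criteria in section 4 include "Abnormal echocardiography before radiotherapy defined as: LVEF<50%; longitudinal strain" with a limit of -16%, and the local ECHO-ST CRF repeats this ("In case of abnormal echocardiography before radiotherapy defined as: LVEF<50%; longitudinal strain", same limit). Section 9.2 plans on a baseline mean of -16.5%, SD 2.1.

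**Comparisons bearing on attribution.** Section 1.7: "Differences in biomarkers between unexposed and paired exposed groups (e.g. right vs. left-sided breast RT) at different time points are analysed". Stage II adds dose-response models.

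**Blood markers.** Section 3.2.2 makes a significant change in each marker between time points an endpoint, with no alpha level and no adjustment.

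**The concern.** The three definitions differ in region (global, or global and segmental), in logic (and, or) and in time (24 months, 6 to 24 months, unstated). The same data could meet one and fail another, and with no order of precedence the choice could be made after the results are known. The same holds for the choice among the three methods.

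The baseline limit raises a separate problem. Strain is measured with error and varies within a woman, so a group selected for values on one side of a cut-off tends to drift back towards the screened mean at the next measurement. The drift needs no radiation effect, yet a before-after test against zero counts it as change.

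For blood markers, an endpoint defined by significance in each of many markers will produce some positive findings by chance.

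**Working it through.** **1. The plan's own figure.** 250 cannot be derived from the stated inputs, because section 9.2 gives the between-patient SD (2.1) but no SD of change and no loss rate. The relative reading of 2.5% is 0.025 × 16.5 = 0.4125 points. Take SD of change = 2.1 × √(2(1 - ρ)), with ρ the within-patient correlation (assumed).
- ρ = 0.5 gives SD of change 2.1 and n = ((1.96 + 0.84) × 2.1 / 0.4125)² ≈ 204 pairs, or 206 with the t distribution. With an assumed 18% loss, 204 / 0.82 ≈ 249.
- ρ = 0.8 needs 84 pairs and ρ = 0.3 needs 287 (t-based).
- Read as 2.5 strain points, only 5 to 10 pairs are needed over the same range, so 250 fits only the relative reading.

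These figures ignore baseline selection. With magnitudes above 16 kept and ρ = 0.5, the kept mean is 17.87 and the kept SD 1.36. The SD of change is then √((1 - 0.5)² × 1.36² + 2.1² × (1 - 0.5²)) = 1.94. About 176 pairs are needed for 0.4125 points, or 151 for 2.5% of 17.87 (0.447 points).

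**2. The three definitions.**

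| Section | Region | Logic | Time |
|---|---|---|---|
| 1.4 | global and segmental | strain and strain rate | 6 to 24 months |
| 3.2.1 | global | strain or strain rate | 24 months |
| 9.2 | global and segmental | strain or strain rate | not given |

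**3. Baseline selection, no true change.** Assume screened strain magnitudes are normal with mean 16.5 and SD 2.1, with the same mean and SD at follow-up. The standardised cut-off is a = (16 - 16.5) / 2.1 = -0.238, where the normal density is 0.388.
- *Limit read as a magnitude (values above 16 kept).* Fraction kept 0.594. Excess of the kept mean = 2.1 × 0.388 / 0.594 = 1.37. Spurious decrease = (1 - ρ) × 1.37 = 0.96, 0.685 and 0.27 points for ρ = 0.3, 0.5 and 0.8.
- *Limit read as a signed number (values at or below -16 excluded).* The planning mean itself is excluded. Fraction kept 0.406, kept mean 14.49. Spurious increase = (1 - ρ) × 2.01 = 1.40, 1.00 and 0.40 points.
- *Other screened means (magnitude reading, ρ = 0.5).* At means of 18, 19 and 20 the decrease is 0.32, 0.16 and 0.07 points.

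In simulation with 206 pairs, mean 16.5 and the magnitude reading, a paired test against zero declared a decrease in 99.9% of null trials at ρ = 0.5 and 86% at ρ = 0.8. A left-right comparison adjusted for baseline kept its 5.0% error rate under the same selection (4,000 simulations).

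**4. Sensitivity of the left-right comparison.** With 206 patients split evenly (assumed), the difference detectable with 80% power is 2.80 × 2.1 × √(1 - ρ²) × √(4/206) = 0.78, 0.71 and 0.49 points for ρ = 0.3, 0.5 and 0.8.

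**5. Blood markers.** Section 3.2.2 names 7 + 4 + 9 + 5 + 21 = 46 markers, plus DNA methylation. Three post-baseline samples give 46 × 3 = 138 contrasts with baseline. At an assumed 5%, 138 × 0.05 = 6.9 false positives are expected if all are null. Correlation among markers does not change that expectation.

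**The case against.** Several points for the plan stand.

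- *Section 3.2.1 is the natural governing text.* It is the dedicated endpoint section and the most specific, and part of the conflict comes from how the list of abbreviations expands GLS/GLSR. But section 9.2 also says segmental, and no section gives precedence.
- *The plan is not silent on method.* A reader might infer that only a test of medians is offered for an endpoint stated as a mean. That is not so: the planned mixed models estimate means. The gap is that none of the three methods is designated.
- *2.5% is a planning effect.* A reader might infer that the observed decrease must reach 2.5%, which would succeed only half the time at a true 2.5% decrease. No section states such a rule, and sections 1.7 and 9.2 point the other way. What remains is that sections 1.4 and 3.2.1 repeat the figure inside the definition.
- *The "or" need not inflate error.* With two-sided 5% tests counting only decreases, the false-decrease rate for two measures is 3.5% to 4.9% (correlation 0.9 to 0). It reaches 6.8% to 9.75% only with one-sided 5% tests, which no section mentions.
- *Attribution is partly covered.* The specific objective in section 3.1 concerns dose and change, and the left-right and dose-response comparisons are planned. No section claims that a before-after test proves causation. What is missing is a statement that attribution rests on those comparisons, adjusted for baseline strain.
- *The markers are secondary and the aim is to identify candidates.* An exploratory label would therefore be enough. The Stage II selection methods are optional modelling steps and do not control this error.

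**Conclusion.** The concern holds. The conflict among sections 1.4, 3.2.1 and 9.2 and the absence of a designated primary analysis are plain from the text and need no assumption.

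That selection on baseline strain shifts the mean change is also secure whenever repeat measurements are imperfectly correlated. Its direction depends on how the limit is read, and its size rests on assumptions: 0.27 to 0.96 points down or 0.40 to 1.40 up (correlation 0.8 to 0.3) if the section 9.2 mean and SD describe screened women, but 0.07 points down at a screened mean magnitude of 20 and correlation 0.5. A before-after test against zero therefore cannot by itself show a radiotherapy effect. It does not follow that any observed decrease would be an artefact.

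For the markers, the 6.9 expected false positives assume 5% per contrast and no true changes.

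A reader might also infer that 250 women are too few. The documents do not support that: 250 agrees with plausible unstated inputs, and allowing for the selection at correlation 0.5 lowers the requirement. The figure cannot be verified until the SD of change and loss rate are given. This should be corrected, and none of it calls for a redesign.

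**What to change.** 1. Use one primary endpoint in sections 1.4, 1.7, 3.2.1 and 9.2, following the global measure at 24 months in section 3.2.1: change in global longitudinal strain from baseline, in strain points on the absolute value. Make strain rate, segmental and 6-month results secondary.
2. Designate one two-sided 5% primary analysis: either the planned mixed model with its 24-month contrast, which keeps women who have only 6-month follow-up, or a paired t test, which drops them. Keep the Wilcoxon test as a sensitivity analysis.
3. State that 2.5% is relative to the baseline mean and is the planning effect, not a success threshold. Give the assumed SD of change and loss rate.
4. Reconcile the strain limit in section 4 and the ECHO-ST CRF with the planning mean in section 9.2, and state whether the limit is signed or a magnitude.
5. State that a change will be attributed to radiotherapy only on the planned left-right or dose-response comparison, adjusted for baseline strain.
6. For blood markers, apply Benjamini-Hochberg control across the 138 contrasts or label them exploratory. Label methylation exploratory unless its readouts are listed.

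The cost is wording, one baseline-adjusted model and a routine p-value adjustment, with no extra patients or visits. Strain rate loses primary status, single markers need stronger evidence, and the left-right comparison is less sensitive than the before-after test (about 0.71 against 0.41 points at correlation 0.5).
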